7.2.3 Subject Identification and Recruitment

Recruitment and screening method

Subjects for potential recruitment for participation in the study will be identified by screening of the medical record. Identification of eligible patients related to their thyroid cancer will be done by review of the medical record for patients to be seen at the UCLA Endocrine Surgery Clinic. A waiver of HIPAA research authorization is requested for screening using medical records. Patients who meet inclusion criteria on the initial chart review will be introduced to the study during their clinic visit and either consented during the clinic visit or via phone/zoom following their clinic visit. The physician will ask the patient if he/she is willing to hear about the research study, and if the patient agrees, they will then introduce the study to the patient. This will be done in a private clinic office.

Enrolment of study participants

Potential study subjects identified by recruitment procedures will be further screened for eligibility and exclusion criteria by direct patient interview and ultrasound by study physician. If after the interview or

ultrasound the physician determines that the patient has met an exclusion criterion, the patient will be informed that he/she is not eligible for the study.

If after the interview or ultrasound, the physician determines that the patient may still be eligible for the study, however molecular test results needed to determine inclusion criteria are still pending, the physician will introduce the study to the patient in person at the time of the clinic visit. If the patient is interested in learning more about the study, the study team will enroll interested patients who are waiting for results. Once results are returned, if they are not eligible, they will be withdrawn from enrollment. If they are eligible, the study team will contact the patient over the phone or via zoom to conduct the consent process and have the patient complete the consent forms via DocuSign for an electronic signature prior to their surgery.

Process for informed consent

Initial contact will be made with potential subjects by a study physician during the scheduled endocrine surgery visit. During this conversation, physicians will inform the patient about the study and the opportunity to participate in a private clinic room with doors closed.

The physician will ask the patient if he/she is willing to hear about the research study, and if the patient agrees, the physician will then introduce and explain the study to the patient. If the subject chooses to participate, the physician will obtain informed consent. The consent documentation will be sent to the patient, reviewed, and electronically signed in person via DocuSign. Patients will receive a copy of the signed consent documents. Once the document is signed, it will be electronically uploaded to the patient's electronic medical record.

If the patient is potentially eligible for participation but is awaiting results to determine all eligibility criterion are met, the physician will ask the patient if he/she is willing to hear about the research study, and if the patient agrees, the physician will then introduce and explain the study. If the subject is interested in participating, the physician will enroll the interested patient. Once obtained, if the results determine the patient is not eligible, they will be withdrawn from enrollment. If the results confirm eligibility, the study team will contact the patient over the phone or via zoom to conduct the consent process. The consent documentation will be sent to the patient, reviewed, and electronically signed over the phone/zoom via DocuSign. Patients will receive a copy of the signed consent documents and a signed copy will be electronically uploaded to the patient's electronic medical record. We will conduct the same consent procedures for patients who meet all eligibility criteria in clinic, are potentially interested in participating after their physician presents the study in person, but would like more time to consider participating. These patients will be given additional time to consider consenting and will be enrolled but contacted at a later date via phone or zoom by the study team to conduct the consent process.

In other rarer cases, the patient may have their initial consult visit via telehealth with their physician. In such cases, the physician will proceed with the same activities as listed above to determine eligibility. If the patient is interested in hearing about the study, the physician will present the study in their private clinic room via telehealth. If the patient is interested in participating in the study, the physician will either enroll them using DocuSign at the time of the telehealth visit or if additional results are required OR the patient would like more time to consider participating, the patient will be enrolled and our study team will contact them at a later date to conduct the consent process.

During the consent process, investigators will inform the patient about his or her rights, the purpose of the study, the procedures to be undergone, and the potential risks and benefits of participation. It will be emphasized that participation in the study is voluntary and if they choose not to participate, they will receive equal standard of care. Study team members have undergone human subjects research and HIPAA training through the CITI courses, and will further be trained about the specific aspects of this study consent prior to enrollment of subjects. The informed consent is attached below (see attachment A)

7.2.4 Privacy

The research team will obtain informed consent in a private room. The interview, ultrasound, and medical procedures will be conducted in a medical examination room or private inpatient setting such as an operating room.

7.2.5 Target Enrollment

For feasibility studies of randomized control trials, a sample size of 24 to 50 patients is recommended. We hypothesize that 50% of intermediate-risk patients will agree to and complete the treatment as assigned. Therefore, in order to end with a total of 50 patients in the randomization cohort, we will need 100 patients with intermediate-risk disease. The UCLA Endocrine Center is a high-volume tertiary referral center, performing 300 thyroid operations annually. Of these patients, approximately 200 patients per year have localized disease eligible for this study. Based on our clinical volume, this is achievable in a one-year enrollment period.

- Total goal enrollment N = 100
- Total goal enrollment of intermediate molecular risk patients into randomization cohort N = 50

7.3 INTERVENTION

7.3.1 Duration of Participation

Subjects will participate until they conclude a 24-month follow-up visit.

7.3.2 Schedule of Activities

7.3.2 Schedule of A	100171010									
Procedure	Screening Day -7 to -1	Enrollment / First clinic visit Visit 1, Day 1	Surgery	Completion Thyroidectomy Postop day 7 to 14	Follow-up Visit 3, Postop Day 14 +/- 7 days	Endocrine Visit Visit 4, Postop Day 28 +/- 14 days	6-month ± 1 month F/u Visit 4	12-month ± 1 month F/u Visit 5	$18\text{-month} \pm 1 \text{ month}$ $F/uVisit 6$	24-month ± 1 month F/uVisit 7
Informed Consent	X	X								
Demographics	X	X								
Medical history	X	X								
Adverse Event Review and Evaluation	X									X
Physical Exam		X								
Ultrasound		X			X		X	X	X	X
Randomization		X								
Consent for surgery		X	X	X						
Surgery			X	X						
Lab work: Tg, Tg Ab, TSH						X	X	X	X	X
Assess need for postoperative RAI						X				
Biopsy concerning lesions seen on neck ultrasound							X	X	X	X
										_

7.3.5 Randomization Protocol

Patients with intermediate molecular-risk thyroid nodules will be randomized to thyroid lobectomy or total thyroidectomy. We will perform a 1:1 randomization in a consecutive manner. Patients will be informed of what operation they will receive and providers will also be aware what operation was performed as it dictates care moving forward. Details of operative management will be discussed further.

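### The allocation method is not specified and concealment is not described, so the next operation could be foreseen and the pilot's drop-out and escalation rates could be biased

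*Combined protocol and SAP*

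**What the plan says.** The method of allocation is covered in one sentence of Section 7.3.5: "We will perform a 1:1 randomization in a consecutive manner". The same section makes the trial open-label: "Patients will be informed of what operation they will receive and providers will also be aware what operation was performed". The available text does not say how the sequence is generated, whether it is blocked or stratified, who holds it, or when an assignment is released. REDCap appears only as the study database (Section 7.4.2).

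On recruitment, Section 7.2.3 says: "Initial contact will be made with potential subjects by a study physician during the scheduled endocrine surgery visit". For patients who decide at the visit, "If the subject chooses to participate, the physician will obtain informed consent". For patients whose molecular result is pending, "If the results confirm eligibility, the study team will contact the patient over the phone or via zoom to conduct the consent process". Those who want more time are handled in the same way. The schedule in Section 7.3.2 marks randomization in one column only, "Enrollment / First clinic visit Visit 1, Day 1".

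Agreement to randomization and completion of the assigned operation are the feasibility endpoints in Section 2 and in Section 5, Aim 2. Section 7.5 lists enrollment, drop-out after randomization and escalation in the lobectomy arm. Section 9.3 uses the completion-thyroidectomy rate in a stopping rule.

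**The concern.** A pilot of this kind measures how many patients accept an operation chosen by chance and then go through with it. That measurement is sound only if neither patient nor recruiter can know the arm before the patient is committed. The plan does not secure this. If the next arm is foreseeable, a patient who will accept only one operation can be approached or consented when that operation is next, and passed over otherwise.

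Aim 2 itself expects reluctance: it anticipates that many patients will resist being randomized or resist the arm they draw. The results are meant to shape a multicentre trial in which allocation would presumably be concealed, so a drop-out rate obtained with foreknowledge would not carry over. The escalation rate is also exposed, because it depends on which patients enter the lobectomy arm.

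**Working it through.** **1. The plan's own figure.** Section 7.2.5 assumes that 50% agree and complete, and wants 50 in the randomization cohort: 50 / 0.50 = 100 intermediate-risk patients. This reproduces the stated number. It is not in dispute, and the fix leaves it unchanged.

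**2. Order of events.** Section 7.3.2 places randomization at Visit 1. Section 7.2.3 lets consent follow that visit, by phone or video, when results are pending or the patient wants time. The two do not fix which comes first for those patients, and nothing ties release of the assignment to a signed consent.

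**3. How far the next arm could be foreseen.** Take 50 allocations and an observer who knows all earlier ones.
- Strict alternation: the first is a guess and the other 49 are known, so (0.5 + 49) / 50 = 99% are guessed correctly.
- Simple randomization: 50%.
- Random blocks of 4 and 6, guessing the arm with fewer patients so far and not knowing the block sizes: 69% (simulation of 20,000 trials).

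**4. Effect on the rates.** The inputs here are assumptions; the documents give none. Of 100 intermediate-risk patients, *a* accept either arm and complete, *b* accept one arm only (half each way), and the rest refuse. A fraction *q* of the one-arm-only patients agree when allocation is concealed, and half of those draw the wrong arm and drop out.
- Concealed: agreement = a + qb; drop-out = (qb/2) / (a + qb).
- Fully foreseen, with one-arm-only patients entered only when their arm is next: agreement = a + b/2; drop-out = 0.

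| a | b | q | Concealed: agreement | Concealed: drop-out | Foreseen: agreement | Foreseen: drop-out |
|---|---|---|---|---|---|---|
| 40 | 20 | 0.25 | 45% | 2.5/45 = 5.6% | 50% | 0% |
| 40 | 20 | 0.5 | 50% | 5/50 = 10.0% | 50% | 0% |
| 40 | 20 | 1 | 60% | 10/60 = 16.7% | 50% | 0% |
| 40 | 10 | 0.25 | 42.5% | 1.25/42.5 = 2.9% | 45% | 0% |
| 30 | 40 | 0.25 | 40% | 5/40 = 12.5% | 50% | 0% |
| 30 | 40 | 1 | 70% | 20/70 = 28.6% | 50% | 0% |

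Over the range tried (a from 30 to 50, b from 10 to 40), concealed drop-out runs from 2.9% to 28.6%. The change in agreement is b(0.5 − q), from 40 × 0.25 = +10 points to 40 × (−0.5) = −20 points.

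**5. Partial foreknowledge.** If the recruiter is right only 70.8% of the time, the case a = 40, b = 20 gives drop-out of 10 × 0.292 / 50 = 5.8%. That is below the concealed 10.0% and 16.7%, but slightly above the concealed 5.6%. Understatement is therefore a tendency, clearest when foreknowledge is full.

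**6. Scale.** Zero drop-outs in 50 has an exact 95% interval of 0% to 7.1%, and 5 in 50 has 3.3% to 21.8%. A pilot reporting 0 of 50 because of steering would appear to rule out a drop-out of 10%.

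**The case against.** The strongest reply is that *consecutive* most naturally means that eligible patients are randomized as they arrive. Sections 7.1 and 7.3.5 both call the study randomized, and alternation is not randomization. That is fair. A reader might infer that the trial will alternate or use an open list, but the documents say neither. They leave it open, and what stands is that no text rules it out.

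A reader might also infer that recruiters see the whole running sequence. Section 7.3.5 says only that providers will know which operation was performed. In a single clinic, wider knowledge is plausible but inferred. Nor is consent always taken by the physician, since the later phone or video consents fall to the study team.

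Knowing the operation after allocation is unavoidable in surgery and is not the defect. The pilot label does not answer the point either, because willingness to accept an unknown arm is what this pilot measures. Sections 7.3.3 and 7.3.4 and the attachments are not in the available text; the titles of those two sections do not concern allocation.

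**Conclusion.** The point holds as a possible bias, not an established one. Allocation is not shown to be concealed, and one literal reading of the rule makes 49 of 50 assignments known in advance. Drop-out would then tend to be understated: about 3% to 29% concealed, against about 0% with full foreknowledge and perfect timing. Those figures rest on the assumed preference model. The case mix of the lobectomy arm could also be distorted, and with it the escalation rate (Section 7.5) and the completion-thyroidectomy stopping rule (Section 9.3). The size of that effect cannot be calculated from the documents.

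Two stronger conclusions are tempting. A reader might infer that foreknowledge inflates agreement; in the model it moves from +10 to −20 points, so no direction can be claimed. A reader might also infer unequal arms; strict alternation gives 25:25 in 50 patients, and only patient characteristics could differ.

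**What to change.** Replace the sentence in Section 7.3.5 with text such as:

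> Patients are allocated 1:1 from a computer-generated sequence, loaded in the REDCap randomization module by a team member not involved in recruitment. The sequence is not accessible to recruiters. The assignment is revealed only after eligibility is confirmed and consent is signed.

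Reconcile Sections 7.2.3 and 7.3.2 so that randomization follows signed consent for every patient, including those who consent after Visit 1.

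Concealment is the essential part; the type of sequence is a choice. Randomly varying blocks keep the numbers close, but their sizes should stay out of the protocol and be undisclosed to recruiters, since even 4/6 blocks are 69% guessable to someone tracking past assignments. Simple randomization is not guessable, but carries a chance of 2 × P(Binomial(50, 0.5) ≤ 20) = 0.203 of a 20:30 split or worse.

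The cost is one paragraph and a small set-up task in a database already in use, assuming its randomization module is available. The targets of 100 and 50 are unchanged, with no extra patients or visits.

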7.3.6 Peri-operative Protocol

Thyroid Lobectomy

Patients undergoing thyroid lobectomy will have the thyroid lobe containing the cancer removed in the standard surgical technique. These operations will be performed at either the UCLA Health Westwood

Ambulatory Surgery Center, UCLA Ronald Reagan Medical Center, or UCLA Santa Monica Medical Center. Patients will undergo our usual postoperative care, which involves:

- Patient's pathology will be sent as "Rush Pathology," such that results return in 48 hours and not the usually 2-week period.
- Patients will have a 4-hour observation in the post-anesthesia care unit and if the operative site appears well, without signs of hematoma formation, they will be discharged the same day.
- If patients are coming from far away (>30 miles from the hospital) or does not have an adult who can stay with them for the next 24 hours, they will stay at the facility overnight for observation.
- Patients will not receive any postoperative thyroid hormone supplementation at this time.

Total Thyroidectomy and Completion Thyroidectomy

Patients undergoing total thyroidectomy will have their whole thyroid gland removed in the standard surgical technique. Patients undergoing a completion thyroidectomy will have their remaining thyroid lobe removed. These operations will be performed at UCLA Ronald Reagan Medical Center or UCLA Santa Monical Medical Center. Patients will undergo our usual postoperative care, which involves:

- If patients are coming from far away (>30 miles from the hospital) or does not have an adult who can stay with them for the next 24 hours, they will stay at the facility overnight for observation.
- Started on calcium carbonate 1g per mouth every 6 hours
- Parathyroid hormone (PTH) level checked 1-hour after operation
 - o If PTH < 10: start calcitriol 0.25mcg per mouth every 6 hours and increase calcium carbonate to 1.5g per mouth every 6 hours
 - If PTH 10 15: start calcitriol 0.25mcg per mouth every 6 hours
 - \circ If PTH > 15: no new medications
- Calcium level will be checked at 4am on postoperative day 1
- The morning after the operation, patients will be started on levothyroxine 1.8 x weight (kg), closest to the available doses (88, 100, 112, 125, 137, 150, 175, 200 mcg). Patients will be prescribed the same dosage on discharge.
- Patient's discharge medication, in addition to the levothyroxine, will be determined on the PTH level drawn previously
 - o If PTH < 10: Calcium carbonate 2g by mouth THREE times a day and calcitriol 0.25mcg by mouth THREE times a day
 - \circ If PTH 10 15: Calcium carbonate 2g by mouth TWO times a day and calcitriol 0.25mcg by mouth TWO times a day
 - o If PTH > 15: Calcium carbonate 1g by mouth TWO times a day

7.3.7 Indications for Postoperative RAI and Completion Thyroidectomy

Indications Postoperative RAI

Patients who ultimately result with aggressive disease on histopathology will need postoperative RAI to reduce the risk of disease recurrence, which is in accordance with the 2015 ATA Guidelines. Indications include:

- Gross extrathyroidal extension of the cancer seen at time of operation
- Lymph node metastasis, which is defined as
 - o 1 or more lymph node with a > 2mm metastasis
 - o 5 or more lymph nodes with a \leq 2mm metastasis
 - o Extranodal extension of metastasis

- Aggressive histology (diffuse sclerosing, insular, Hurthle cell, solid, hobnail, columnar cell variant, and high-grade follicular cancer)
- Multifocal vascular invasion
- Microscopic margin positivity

Completion Thyroidectomy

Patients who initially underwent thyroid lobectomy and pathology ultimately return with the indications listed above for postoperative RAI need to undergo completion thyroidectomy. All patients who undergo thyroid lobectomy have their pathology sent for rush pathology, which will result 48 hours later. If patients need a completion thyroidectomy, the surgeon will call them with this information and book a second operation. The surgical team will perform informed consent for the operation on the day of the surgery and patients will receive the usual peri-operative care as listed above.

7.3.8 Postoperative RAI Dosing

At the visit with the endocrinologist 4-6 weeks postoperatively, patients will have the first set of thyroglobulin (Tg) and thyroglobulin antibody (Tb Ab) drawn. If patients initially met criteria for RAI based on pathology, but their Tg and Tg Ab ultimately return as undetectable, these patients will not receive RAI. Patients who ultimately need postoperative RAI will be dosed according to the 2015 ATA guidelines.⁵ It recommends a low-administered activity of 30 mCi.

7.3.9 Goal TSH Suppression Levels

Postoperative thyroid hormone doses will need to be adjusted by endocrinologists corresponding to the ideal TSH level in accordance with the 2015 ATA Guideline.⁵

The ideal TSH levels will be as followed:

- If patient underwent RAI, goal TSH = 0.1 0.5
- If patient did not undergo RAI, goal TSH = 0.5 2.0

Initial labs, which include TSH, thyroid function test, Tg, and Tg antibody will be drawn 6-8 weeks postoperatively in time with the first postoperative endocrinology visit. During this visit is when thyroid hormone medication will be adjusted according to goal TSH and need for postoperative RAI will be determined.

7.3.10 Surveillance Protocol

All surveillance visits will be done at the UCLA Endocrine Surgery office. These visits are to assess for any evidence of early cancer recurrence. Visits will be done at 6-, 12-, 18-, and 24-months postoperatively. All surveillance visits will have a window of 1 month. The visit will include:

- History and physical exam
- In-clinic ultrasound assessing the postoperative thyroid bed, central neck, and lateral necks to assess for recurrence
- If there are any concern for disease recurrence on the ultrasound, an in-office FNA will be performed. Indications for FNA include
 - Lymph node >1cm in size
 - o Thyroid-appearing tissue >1cm in size located in the postoperative thyroid bed
- Lab draw: TSH, thyroid function test, Tg, Tg antibody

7.4 DATA MANAGEMENT

7.4.1 Data Collection

Patient's data will be collected via review of the patient's electronic medical record (EMR), which will be reviewed weekly. Data points to be recorded include:

- Patient demographics: age, sex, BMI, date of birth
- Comorbid endocrine disease: concurrent hypo/hyperthyroid disease, parathyroid disease, neuroendocrine tumor
- Prior or current cancer diagnosis
- Medications
- Bethesda category of FNA
- ThyroSeq results (specific mutation(s) present, cancer risk classifier results)
- Type of operation (thyroid lobectomy, total thyroidectomy, completion thyroidectomy)
- Ultrasound imaging results
- Laboratory values (Tg, Tg antibody, TSH, Calcium, PTH)
- Pathology results
- RAI dosing
- Thyroid hormone medication dosing
- Presence of postoperative complications: neck hematoma, reoperation, hypocalcemia, recurrent laryngeal nerve injury, voice hoarseness, readmission, reason for readmission

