2. ABSTRACT

Every year, ~45,000 individuals in the United States develop a new diagnosis of thyroid cancer. Initial therapy for most patients involves surgical excision of the thyroid lobe containing the cancer (thyroid lobectomy) or removal of the entire gland (total thyroidectomy). Compared to thyroid lobectomy, total thyroidectomy carries double the risk of recurrent laryngeal nerve injury, adds the possibility of permanent hypoparathyroidism, and makes all patients dependent on lifelong thyroid hormone supplementation. We accept these additional risks because total thyroidectomy allows patients to receive postoperative radioactive iodine (RAI) therapy, which mitigates recurrence risk in high-risk patients. Thus, total thyroidectomy primarily benefits patients that require radioiodine remnant ablation. Unfortunately, the need for RAI ablation relies on postoperative pathology findings and cannot be reliably predicted preoperatively. The current problem is that some patients in this system receive overly aggressive care, undergoing the additional risk of total thyroidectomy but ultimately not requiring radioactive iodine. Others may receive overly conservative initial treatment, needing reoperation for a completion thyroidectomy after initial thyroid lobectomy. Thus, there is a clear, unmet need for preoperative prognostic risk stratification to determine ideal surgical treatment for thyroid cancer.

One potential solution is to risk-stratify thyroid cancer patients based on molecular testing. Currently, molecular analysis is used to differentiate benign nodules from potentially cancerous nodules but it is not utilized for prognostic purposes. Several studies have determined that high-risk mutation profiles, such as *TERT* and *TP53*, ^{1,2} predict metastatic and recurrent disease. As such, if mutation status was known preoperatively, these patients could be directed to undergo a total thyroidectomy. Conversely, lower risk lesions could be directed to thyroid lobectomy. There would still be a large area of uncertainty among intermediate molecular-risk lesions, such as isolated *BRAF*, ³ for which there are no recommendations on extent of treatment.

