Thyroidectomy for thyroid cancer. Most patients can either undergo thyroid lobectomy or total thyroidectomy as initial surgical treatment of their thyroid cancer. For patients with disease involving the lymph nodes or soft tissues of the neck, total thyroidectomy is indicated so that patients can receive postoperative treatment with RAI. Thus, it is important for patients with diagnosed thyroid cancer to undergo ultrasound of the neck to assess for sonographic evidence of extrathyroidal spread and lymph node metastasis.5 For cancers < 1 cm limited to the thyroid, thyroid lobectomy is sufficient because those patients do not benefit from RAI. However, those who fall in the middle with nodules between 1 cm and 4 cm without evidence of disease spread, which accounts for most thyroid cancer patients, the ideal extent of surgery is uncertain and frequently debated. Since total thyroidectomy has a higher risk of recurrent laryngeal nerve injury and hypoparathyroidism, and renders all patients hypothyroid, it should be avoided if there is no clinical benefit.

Postoperative RAI for high-risk disease on pathology. Patients who ultimately end up with high-risk disease on pathology (extrathyroidal extension, numerous lymph node involvement, high-risk histologic features, etc.) undergo RAI therapy. In order to receive RAI, patients must have a total thyroidectomy. Those who initially had thyroid lobectomy and pathology returns with high-risk disease undergo reoperation for completion thyroidectomy – removal of the remaining thyroid gland – prior to starting RAI. The response to therapy is then assessed based on thyroglobulin levels, which are proteins secreted by thyroid tissues. Complete response would mean patients have undetectable serum thyroglobulin levels. As such, patients can be monitored for disease recurrence by serially checking thyroglobulin levels.

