8 RISKS AND BENEFITS

8.1 Risks to Subjects and Mitigating Steps

If patients had their FNA performed at a facility outside of UCLA, we will not have their sample and therefore will need to undergo repeat FNA of the nodule to participate. Informed consent will be separately obtained for the FNA. Risks of FNA include <1% risk of bleeding, pain, infection, or damage to surrounding structures. To mitigate this risk, we will ensure that the FNA are performed by physicians who have had appropriate training. Standard procedures will include sterilization of the puncture site and use of sterile materials to minimize infection risk.

There is equipoise in performing a thyroid lobectomy or total thyroidectomy for intermediate molecular-risk thyroid cancer, and both are currently offered for these patients. Both operations carry risk of bleeding and infection. Total thyroidectomy has an increased risk of injury to the recurrent laryngeal nerve causing voice hoarseness compared to thyroid lobectomy and makes all patients dependent on thyroid hormone medication. Majority of patients who undergo thyroid lobectomy do not require thyroid hormone supplementation, but they carry a risk that the remaining lobe cannot produce enough hormone and thus will be dependent. Patients randomized to thyroid lobectomy may ultimately have high risk histopathology and need postoperative RAI. These patients will need a reoperation for completion thyroidectomy, or removal of the remaining thyroid lobe, and thus are at risk again for the operative complications listed above.

Other risk includes privacy and confidentiality violation with protected health information from unplanned disclosure of HIPAA-protected data. These risks are estimated to be <1%. Mitigating steps we will take are:

- Interviewing and obtaining consent in a secure, private setting
- Use of de-identified, numeric code once data collection is complete. The key for this code will be
 maintained as a single file under password protection and encryption by the study PI. It will not
 be shared with others outside of the institution or study, and will be destroyed at the completion
 of the study.

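### Nerve injury and hoarseness are taken from the chart as present or absent, with no voice item named at any visit, so the plan has no set way to tell temporary from lasting voice change

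*Combined protocol and SAP*

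**What the plan says.** The Abstract (section 2) states that "total thyroidectomy carries double the risk of recurrent laryngeal nerve injury", and adds possible permanent hypoparathyroidism and lifelong hormone dependence. Sections 4 and 8.1 repeat the nerve risk. Section 8.1 ties it to voice: "Total thyroidectomy has an increased risk of injury to the recurrent laryngeal nerve causing voice hoarseness compared to thyroid lobectomy". It also says that patients who need a completion operation face the operative complications again.

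On data, 7.4.1 says: "Patient's data will be collected via review of the patient's electronic medical record (EMR), which will be reviewed weekly". The relevant field records only whether a complication after surgery was present, in a list that ends "hypocalcemia, recurrent laryngeal nerve injury, voice hoarseness, readmission, reason for readmission". Section 7.4.2 has investigators enter these items from the record into REDCap, on a form (attachment C) that is not among the documents.

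In 7.3.2, as it can be read, medical history is marked at screening and Visit 1, and physical exam at Visit 1 only. The column "Follow-up Visit 3, Postop Day 14 +/- 7 days" has ultrasound marked and nothing else. The endocrine visit has laboratory work and the RAI assessment. Adverse event review is marked at screening and at 24 months. Section 7.3.10 lists "History and physical exam" at 6, 12, 18 and 24 months, for the stated purpose of finding early recurrence.

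Section 7.3.5 makes the operation known to patients and providers. Section 9.2 reviews adverse events after every 10 subjects against expected rates, which are not given. Section 7.5 does not list nerve injury among its outcomes.

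**The concern.** Three things are missing from the readable plan for a harm that it uses to motivate the trial: a named voice item before surgery, a prompt to ask about voice at a fixed time afterwards, and a time point that divides temporary from lasting change. Recording only that a complication was present supplies none of them.

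Capture then depends on who happens to ask and write it down. Section 7.3.6 gives the arms different contact after surgery. Lobectomy patients normally leave the same day after 4 hours of observation. Total thyroidectomy patients have a calcium check at 4 am and start levothyroxine the next morning. Lobectomy patients who need completion have a second peri-operative episode. These differences could raise charting in either arm, so the direction of any error cannot be told from the plan.

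At stake are the safety review in 9.2, which relies on these counts, and the descriptive harm data that the pilot leaves behind. The feasibility conclusion is not at stake.

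**Working it through.** **1. Arm size.** Section 7.2.5 expects 50% to agree to and complete assigned treatment and wants 50 in the randomization cohort: 50 / 0.50 = 100, which matches the stated 100. At 1:1 (7.3.5), 50 / 2 = 25 per arm.

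**2. Where voice change could be found, in time order.**

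- Screening and Visit 1: medical history at both, physical exam at Visit 1. No voice item named.
- Visit 3, day 14 ± 7: ultrasound only.
- Endocrine visit, day 28 ± 14: laboratory work and RAI assessment.
- 6, 12, 18 and 24 months: general history and physical exam under 7.3.10, although the physical exam row in 7.3.2 is marked at Visit 1 only.
- 24 months: adverse event review.
- Throughout: weekly chart review (7.4.1) and events experienced or reported by subjects (9.2).

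Hoarseness that resolves before 6 months is therefore recorded only if it is raised and charted without a prompt. Hoarseness that lasts has general opportunities to be noticed, but no named question and no stated voice baseline to compare with.

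**3. Which operation caused it.** Visit 3 runs from day 14 − 7 = 7 to day 14 + 7 = 21. Completion thyroidectomy is scheduled for days 7 to 14, entirely inside that window. A presence-only entry does not show whether the change came before or after the second operation. An onset date does.

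**4. Sensitivity to unequal charting.** The only nerve-risk figure in the documents is the ratio of 2. The capture rates below are assumptions for illustration.

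Observed ratio = 2 × (capture after total / capture after lobectomy)

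- Equal capture: 2.
- 80% after total, 50% after lobectomy: 2 × 0.8 / 0.5 = 3.2.
- 50% after total, 80% after lobectomy: 2 × 0.5 / 0.8 = 1.25.

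**5. What 25 per arm can show even with perfect capture.** The documents give no absolute rate. Assume a lobectomy rate p of 1% to 10%, with 2p after total thyroidectomy. Expected cases are 25p and 50p. The chance of no case in either arm is (1 − p)^25 × (1 − 2p)^25. Power is for Fisher's exact test at two-sided 0.05. The last column is the number per arm for 80% power to compare two proportions.

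| Lobectomy / total | Expected cases | No case in either arm | Power at 25 per arm | Per arm for 80% |
|---|---|---|---|---|
| 1% / 2% | 0.25 / 0.5 | 47% | <0.1% | 2,319 |
| 2% / 4% | 0.5 / 1.0 | 22% | <0.1% | 1,141 |
| 5% / 10% | 1.25 / 2.5 | 2% | 1.3% | 435 |
| 10% / 20% | 2.5 / 5.0 | <0.1% | 8.6% | 199 |

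Across this range the pilot cannot compare the arms. It could not tell 3.2 from 1.25 either, so step 4 shows how a ratio could be distorted and does not forecast what this trial will report.

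**The case against.** The strongest reply is that the trial plans no comparison of nerve injury. Section 7.5 lists enrollment, drop-out and escalation as outcomes. Its secondary endpoints are ATA risk category, hormone need and short-term quality of life. That stands, and it limits the point to safety review and description.

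Second, the plan has opportunities to detect the harm: weekly record review, subject-reported events under 9.2, four surveillance visits with history and examination, adverse event review at 24 months, and separate entries for nerve injury and hoarseness. This also stands. A reader might infer that temporary and lasting injury can never be separated. The documents do not support that, because a persistent problem could well be charted. They support only that no planned way to separate them is set out.

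Third, attachment C was not available and may hold dates or baseline items, and the schedule table came through extraction damaged, so blank cells are weak evidence. Both caveats stand. Dates on a form would still depend on someone asking, and no readable visit prompts the question.

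Fourth, a self-reported item in an open-label trial can itself be biased, and it measures voice change rather than nerve injury. That is correct. Asking everyone the same question at the same times reduces unequal capture and leaves that bias in place.

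**Conclusion.** The point holds as a cheap improvement, not as an error in the design. On the readable documents, nerve injury and hoarseness are presence-only chart items, no visit names a voice item, and nothing planned separates temporary from lasting change or the first operation from the completion operation. In an open-label trial, unprompted charting may differ by arm, in an unknown direction.

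Two further readings go too far. A reader might infer that the case for lobectomy rests mainly on nerve injury, but the Abstract gives three harms, and hormone need is already a secondary endpoint. A reader might also infer that no preoperative history is taken, but 7.3.2 marks medical history at screening and Visit 1. What is missing is a named voice item.

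The size is modest. The ratios of 3.2 and 1.25 rest on assumed capture rates, and the table on assumed absolute rates. The gain is better harm data for the 9.2 review and for description. Power and the feasibility conclusion do not change. The conclusion also assumes that attachment C does not already provide these items.

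**What to change.** - In 7.3.2, add one yes/no voice-change item, asked in the same words in both arms at Visit 1 (baseline), Visit 3 and the 6- and 12-month visits. For patients who have a completion operation, also ask it at the next scheduled visit after that operation.
- In REDCap, record onset and resolution dates unless attachment C already has them.
- Report new voice change descriptively by assigned arm, as resolved or still present at 6 months, with no test between arms.
- Reconcile the physical exam row in 7.3.2 with 7.3.10, which disagree on the surveillance visits.

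The cost is one question at four existing visits, or 50 × 4 = 200 answers if all 50 randomized patients attend, plus one more for each completion patient and at most two date fields. No visit or laryngeal examination is added. The downside is that self-reported voice change is less specific than an examination and can be influenced by knowing the operation, and the report should say so.
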